13.8.2 Overall Survival and Progression-Free Survival

The distributions of progression-free and overall survival will be summarized using the method of Kaplan-Meier. Median times for each therapy arm will be accompanied by 90% confidence intervals based on log(-log(endpoint)) methodology. For cohort 1, the pairwise comparisons between the MEDI4736(durvalumab)/tremelimumab alone and MEDI4736(durvalumab)/tremelimumab with RT arms will be conducted using log-rank tests.

13.8.3 Response per irRC

The proportions of patients with response according to irRC will be presented with 90% exact binomial confidence intervals. For cohort sizes of 30 (cohort 2) and 40 patients (cohort 1), the confidence intervals will be no wider than 0.32 and 0.28, respectively. For cohort 1, the pairwise comparisons of irORR between RT and the control arm will be conducted using chi-squared tests.

13.8.4 Local Control Rate and Abscopal Response Rates

The proportions of patients with local control within the irradiated field will be reported within each RT treatment arm and presented with 90% exact binomial confidence intervals. Similar presentations will be used for abscopal response rates. For cohort sizes of 30 (cohort 2) and 40 patients (cohort 1), the confidence intervals will be no wider than 0.32 and 0.28, respectively.

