1.2 Secondary Objectives

NSCLC Cohort

- To estimate median progression-free survival and overall survival
- To determine local control within the irradiated field(s) and abscopal response rates
- To evaluate associations between PD-L1 expression as well as levels of infiltrating CD3+, CD8+ T-cells and overall response
- To explore changes in changes in PD-L1 expression, circulating T-cell populations, T-cell infiltration, RNA expression, spatial relationship of immune markers, and mutational burden as a result of low or high dose radiation

Colorectal Cohort

- To estimate median progression-free survival and overall survival
- To determine local control within the irradiated field and abscopal response rates
- To evaluate associations between PD-L1 expression as well as levels of infiltrating CD3+ CD8+ T-cells and overall response
- To evaluate changes between PD-L1 expression as well as levels of infiltrating CD3+, CD8+ T-cells induced by targeted low or high dose radiation
- To explore changes in changes in circulating T-cell populations, T-cell infiltration, RNA expression, spatial relationship of immune markers, and mutational burden as a result of low or high dose radiation

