10. STUDY CALENDAR

Baseline evaluations are to be conducted within 4 weeks prior to start of protocol therapy. Scans and x-rays must be done ≤5 weeks prior to the start of therapy. In the event that the patient’s condition is deteriorating, laboratory evaluations should be repeated within 48 hours prior to initiation of the next cycle of therapy. Note that all study visits in the calendar are specified by week, but should be performed on the same day of the week when feasible and every effort should be made to schedule them +/-2 days.

Cohort 1 – Non small cell lung cancer

	Pre- Study	Wk 1	Wk 2	Wk 3	Wk 4	Wk 5	Wk 6	Wk 7	Wk 8	Wk 9	Wk 10	Wk 11	Wk 12	Wk 13- 52	Off Treatment ^e
MEDI4736(durvalumab)		A				A				A				A ^e	
Tremelimumab		B				B				B				B ^e	
Radiation therapy			C				C				C			C ^e	
Informed consent	X														
Demographics	X														
AE/SAE Assessments ^m		X				X				X				X ^e	X
Medical history	X	X				X				X				X ^e	
Concurrent meds ^d	X													X	X
Physical exam	X	X				X				X				X ^e	X
Vital signs ^p	X	X				X				X				X ^e	X
Performance status	X	X				X				X				X ^e	X
CBC w/diff, plts	X	X ^k				X				X				X ^e	X
Serum chemistry ^a	X	X ^k				X				X				X ^e	X
EKG ^j	X														
Hepatitis B and C and HIV ⁿ	X														
Urinalysis	X ⁱ														
Tumor measurements	X		Tumor measurements should be performed during week 7 or 8 and then repeated every 12 weeks +/- 5 days. Documentation (radiologic) must be provided for patients removed from study for progressive disease.												
Radiologic evaluation ^l	X		Radiologic measurements should be performed during week 7 or 8 and then every 12 weeks +/- 5 days while on treatment .												X ^o
B-HCG	X ^b	X				X				X				X ^e	X ^e
Head MRI ^{dh}	X													X ^d	
Research blood samples	X					X									
Biopsy of site(s) of disease	X ^f							X ^g							
PRO-CTCAEⁿ	X		X		X		X		X				X	X	X

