	
A: MEDI4736(durvalumab): Administered intravenously at a dose of 1500mg every 4 weeks for a maximum of 13 doses.
 
B: Tremelimumab: Administered intravenously at a dose of 75mg every 4 weeks for a maximum of 4 doses.
 
C: Radiation therapy: Administered only on week 2 for Arm A (high dose radiation) and every 4 weeks for a maximum of 4 times in Arm B (low dose radiation)
 
a: Albumin, alkaline phosphatase, total bilirubin, bicarbonate, BUN, calcium, chloride, creatinine, glucose, LDH, phosphorus, potassium, total protein, SGOT [AST], SGPT [ALT], sodium. Also amylase, creatinine clearance, gamma glutamyltransferase, lipase, and magnesium, CPK, TSH. Free T3 or free T4 also measured if TSH is abnormal or if there is clinical suspicion of an AE related to the endocrine system. .
 
b: Serum pregnancy test (women of childbearing potential). Women of child-bearing potential must have a negative serum beta-HCG pregnancy test during screening and a negative urine beta-HCG pregnancy test within 24 hours of starting treatment.
 
c: Every 12 weeks during weeks 12-52 and then 30,60, 90 days after discontinuation
 
d: Every 12 weeks
 
e: Every 4 weeks
 
f: Archival tissue may be used in place of biopsy in this cohort.
 
g: To be performed week 7 or 8. Optional in patients with irradiated lesions outside the liver. For patients who receive radiation to the liver, this second biopsy is required unless unsafe to perform.
 
h: Head CT may be substituted for MRI if patient cannot tolerate MRI. Subsequent MRI's to be performed only if previously treated brain metastases or when clinically indicated.
 
i: At baseline (screening) and then as clinically indicated.
 
j: Abnormal findings should be repeated and require appropriate clinical evaluation. Normal EKGs do not require repeating.
 
k: If screening laboratory assessments are performed within 3 days prior to Day 1 (first infusion day), they do not need to be repeated at Day 1
 
l: CT Chest, Abdomen, and Pelvis (CAP)
 
m: During scheduled history and physical exams and during monitoring of AE's, attention should be paid to the side effects resulting from radiation and any potential enhancement of these due to the administration of immunotherapy.
 
n: Negative serologies over the preceding year may replace screening study
 
o: when off treatment for reasons other than progression after week 7-8, until week 52.
 
p: Vital signs timepoints for infusions are pre-dose, every 30 minutes; post-dose 30 and 60 minutes (+/- 10 minutes)
 
q: PRO-CTCAE items to be completed at baseline, every 2 weeks for 8 weeks and then every 4 weeks for a total of 8 cycles. All patients on any arm of study will answer the same list of PRO-CTCAE questions.

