11.3.6 Immune-Related Best Overall Response Using irRC (irBOR)

irBOR is the best confirmed overall response over the study as a whole, recorded between the date of first dose until the last tumor assessment before subsequent therapy (except for local palliative radiotherapy for painful bone lesions) for the individual subject in the study. For the assessment of irBOR, all available assessments per subject are considered.

irCR or irPR determinations included in the irBOR assessment must be confirmed by a second (confirmatory) evaluation meeting the criteria for response and performed no less than 4 weeks after the criteria for response are first met.

11.3.7 Local response is defined as irRC applied to the irradiated lesions. This is not applicable in the case of an irradiated bone lesion.

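### Local control (13.8.4) is an untimed crude proportion, although systemic progression decides how long each patient's irradiated field is imaged, so the rate partly reflects when imaging stopped

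*Combined protocol and SAP*

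**What the plan says.** Section 1.2 makes local control a secondary objective in both cohorts; for NSCLC it reads "To determine local control within the irradiated field(s) and abscopal response rates".

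Section 13.8.4 gives the whole analysis: "The proportions of patients with local control within the irradiated field will be reported within each RT treatment arm", "presented with 90% exact binomial confidence intervals". On precision, for arms of 30 and 40 patients, "the confidence intervals will be no wider than 0.32 and 0.28, respectively". Local control itself is not defined. The nearest text is 11.3.7: "Local response is defined as irRC applied to the irradiated lesions". That covers local response. Section 13.8.2 plans Kaplan-Meier estimates for PFS and OS only.

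On imaging, the study calendar (section 10) says "Radiologic measurements should be performed during week 7 or 8 and then every 12 weeks +/- 5 days while on treatment". Its footnote o limits off-treatment scans to patients seen "when off treatment for reasons other than progression after week 7-8, until week 52"; the footnote stands under both cohort tables. Section 5.8 lets the site repeat imaging about 4 to 8 weeks after first PD, and treatment stops if PD is confirmed. Section 5.5 follows everyone for at least a year, but nothing requires the field to be imaged after progression.

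**The concern.** A binomial proportion is interpretable when every patient is observed over the same window. Here the window closes when systemic disease progresses. A patient who progresses at the week 7 or 8 scan may have the field imaged once or twice; a patient with durable systemic control has it imaged several times. In-field progression after the last required scan is not observed.

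The reported rate therefore mixes two things: how well radiation held the lesion, and how early imaging ended. Two dose arms with the same local control but different systemic progression can show different rates. The radiation schedules add to this. In Arm A the week 7 or 8 scan follows the single course. In Arm B, with courses at weeks 2, 6, 10 and 14 (section 5.1), it falls between the second and third courses.

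**Working it through.** **1. The plan's own figure.** The two-sided 90% Clopper-Pearson interval is widest at x = n/2. For n = 30, x = 15 it runs from 0.339 to 0.661, width 0.322. For n = 40, x = 20 it runs from 0.361 to 0.639, width 0.278. Both match the stated 0.32 and 0.28. The arithmetic is right, but it presumes that every patient gives a fully observed yes or no.

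**2. Inputs.** From the calendar: scans at about weeks 7.5, 19.5, 31.5 and 43.5. The documents give no PFS or local-failure rate for these arms, so the following are assumptions:
- median systemic PFS of 2 to 6 months (8.67 to 26 weeks), exponential;
- exponential local failure with true 6-month control of 0.60, hence 12-month control of 0.60² = 0.36;
- local and systemic failure independent, death ignored, time counted from start of treatment;
- the last scan is the first one at or after systemic progression;
- a patient with no in-field failure by the last scan counts as controlled.

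**3. Formula.** Crude rate = Σ P(last scan = s) × 0.60^(s/26), where P(no systemic progression by s) = 2^(−s/median).

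| Last scan (week) | True local control at that scan | P(last), median PFS 2 mo | P(last), median PFS 6 mo |
|---|---|---|---|
| 7.5 | 0.863 | 0.451 | 0.181 |
| 19.5 | 0.682 | 0.339 | 0.224 |
| 31.5 | 0.539 | 0.130 | 0.163 |
| 43.5 | 0.425 | 0.081 | 0.432 |

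- 2 months: 0.389 + 0.231 + 0.070 + 0.034 = **0.724**.
- 6 months: 0.156 + 0.153 + 0.088 + 0.184 = **0.581**.
- Medians of 3 and 4 months give 0.67 and 0.63.

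The lesion-level truth is identical throughout, yet the reported rate moves by about 14 points. The arm with worse systemic control looks better.

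**4. Direction.** Against 12-month control (0.36) the excess is 0.36 down to 0.22. Against 6-month control (0.60) it runs from +0.12 to −0.02. With true 6-month control of 0.80 (12-month 0.64), the crude rate is 0.864 / 0.833 / 0.810 / 0.781 at medians of 2 / 3 / 4 / 6 months. Adding one confirmatory scan 4 weeks after PD lowers these to 0.835 / 0.807 / 0.787 / 0.762, all still above 0.64.

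**5. Dependence on the counting rule.** Take a median PFS of 3 months and true 6-month control of 0.80. If 10% are never scanned and count as failures, 0.833 × 0.90 = 0.75; at 20%, 0.833 × 0.80 = 0.67. If they count as controlled, the rates are 0.85 and 0.87.

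**6. A timed, censored estimate.** With true 6-month control of 0.60, a Kaplan-Meier estimate censored at the last scan recovers true control at each scan under independence (0.683 against 0.682 at week 19.5). At correlation 0.5 and a median PFS of 2 months it gives about 0.75 there, so it is still optimistic.

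**The case against.** The strongest reply is that the plan only lacks a definition. If local control means best local response under irRC, a proportion with an exact interval matches the format of 13.8.3. Under 11.3.6, irCR and irPR need confirmation at least 4 weeks later, so a patient scanned once could count only as stable. If unassessable patients were failures, as 13.9.2 has it for overall response, the rate would be pushed down. The estimate is also descriptive: 13.8.4 plans no test between arms, and the primary endpoint excludes irradiated lesions.

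Much of this stands. A reader might infer that patients scanned once count as controlled and that the rate is overstated. The documents do not say the first, and the second depends on the landmark and on the missing rule. Nor is a single scan certain, because 5.8 allows a confirmatory scan and continued imaging if PD is not confirmed. An expected response rate of 5% to 22% does not show that most patients progress by week 8, since stable disease is also non-response. Deaths are not lost either, since all patients are followed for at least a year.

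What survives is that a definition alone does not equalise the windows. Any reading of control as absence of in-field progression needs a time point and a rule for patients whose imaging has ended.

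**Conclusion.** The concern holds in this limited form: an untimed binomial proportion is the wrong summary when systemic progression sets each patient's observation window, and the plan leaves the counting rule open. If patients without observed in-field progression count as controlled, the same true 6-month control of 0.60 is reported as about 0.72 at a median PFS of 2 months and 0.58 at 6 months. In all scenarios run under that rule, the rate exceeds 12-month control. No general statement of overstatement is supported: against 6-month control the sign varies, and counting unscanned patients as failures can reverse it. The sizes rest on assumed exponential PFS and local-failure rates that the documents do not give. The matter affects a descriptive secondary objective; the primary endpoint and the stopping rules are untouched.

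**What to change.** Revise 13.8.4 as follows.

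- Define local failure as irPD of the irradiated lesion(s), and name the reference: 11.3.3 measures irPD from nadir, 11.3.5 from baseline.
- Set the denominator as patients who started RT, and the time origin as first radiation.
- Report the cumulative incidence of local failure per RT arm with a 90% CI, at a landmark tied to the second scheduled scan (about week 19 to 20). That is also the first scheduled scan after all four Arm B courses.
- Censor at the last scan showing the field. Count as a competing event any death without local failure within a stated window after that scan, for example the 12-week rule already used for PFS in 13.2.2.
- State that censoring at systemic progression may be informative, and report how many patients have only one post-radiation scan.
- Keep best local response by irRC as a separate descriptive proportion.
- Give a 6-month figure only with numbers at risk.

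The cost is SAP wording and a standard estimator on planned scans. The interval will be wider than 13.8.4 states, and few patients remain at later times. In the model above with 6-month control of 0.60, the share still at risk for the second scan is 0.549 × 0.863 = 0.47 (median PFS 2 months) to 0.819 × 0.863 = 0.71 (6 months), or about 19 to 28 of 40. For the third scan it is 0.210 × 0.682 = 0.14 to 0.595 × 0.682 = 0.41, or about 6 to 16 of 40. Some optimism remains if local and systemic failure are correlated.

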13.8.5 Prognostic Effect of PD-L1 Expression

The prognostic effect of PD-L1 expression within the tumor microenvironment will be investigated for each treatment arm. Each patient will be retrospectively classified according to pre-treatment PD-L1 expression (positive or negative). Clinical response (CR or PR vs. SD/PD/Unevaluable) will be compared according to PD-L1 expression using Fisher's exact tests.

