CLIA approved laboratory. We have published the methods, protocols, and data establishing the sensitivity and specificity of immunohistochemical staining (IHC) assays using the monoclonal antibodies recognizing PD-L1 (CD274, B7-H1) and other antibodies mentioned above including the standard CD3, CD4, and CD8 lymphocyte markers in several recent manuscripts [78, 79, 87-89].

Following chromogenic IHC for PD-L1 we will score the percentage of cells staining positively for PD-L1. In addition, an intensity score, reflecting the average positive staining intensity on a 0-3 scale will be determined and used to calculate a modified H-score (range 0-300).

Publications to date have determined various cut-points as the optimal for predicting clinical response to immune checkpoint therapy (1%, 5%; 50%). We examine these cut-points in an initial examination of our data. The percentage of positive staining cells and the modified H-score will also be analyzed as continuous variables for optimized thresholds as exploratory endpoints.

Spatial quantification of the tumor microenvironment

In addition to PD-L1 and tumor infiltrating lymphocytes, other immune markers such as PD-L2 and CD68 may also indicate tumor mediate immune regulation and could also predict response to immune therapy either alone or in conjunction with other markers. Additionally, while traditional immunohistochemistry generally only allows for the evaluation of one or two proteins at a time, multiplex immunofluorescence (IF) simultaneously evaluates expression and provides more quantifiable spatial resolution for multiple biomarkers. Our initial work has demonstrated the reproducibility of this technique in identifying various populations of tumor infiltrating lymphocytes, as well as PD-L1 expressing tumor cells and PD-L1 and PD-1 expressing infiltrating lymphocytes; therefore we propose to use multiplex IF to explore associations between response and expression of PD-1/PD-L1 in the tumor versus tumor/stroma interface, as well as co-localized PD-L1 / PD-1 expression.

Mutational Burden

WES will be performed by DFCI CIMAC Translational Immunogenomics Lab led by [name] according to CIMAC approved protocols.

RNA seq

RNA extraction and integrity will be performed by DFCI CIMAC Translational Immunogenomics Lab led by [name] and by UC Davis under the direction of [name].

CyTOF.

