13.8.6 Prognostic Effect of T-cell infiltration

The prognostic effect of infiltrating CD8+ T-cells within the tumor microenvironment will be investigated for each treatment arm. Each patient will be retrospectively classified according to pre-treatment infiltration (positive or negative). Clinical response (CR or PR vs. SD/PD/Unevaluable) will be compared according to infiltration using Fisher's exact tests.

Paired biopsies are mandated in the colorectal arm and also in lung cancer patients that receive liver directed radiation unless there are concerns regarding safety. To give a sense of power for studies to be done on paired tissue, differences will be taken for all measures and the hypotheses is that biomarkers if PD-L1 expression and T-cell infiltration will increase (measured as a continuous quantitative variable) post therapy. Thus, assuming that within each cohort we will obtain post treatment biopsies of at least 25 patients, using a two-sided 0.05 level paired t-test there is at least 80% power to detect a 0.59 SD change in mean of a quantitative correlative parameter using a two-sided test with 5% type I error. Quantitative measure will be transformed to attain normality or appropriate non-parametric tests will be conducted. Power for these tests will be further improved if a greater percentage of paired biopsies are obtained. We will obtaining biopsy samples from participating sites as the trial proceeds and will continuously monitor the percentage of patients for whom a post treatment biopsy is not obtained so we can try to address any issues or questions regarding this. Our plan is to pursue paired tissue analyses separately within each cohort, but since a goal of the study is to more generally evaluate the impact radiation on PD-L1 expression and tumor infiltrating lymphocytes, if needed we can consider analyses that combine data from the 2 cohorts of patients if numbers are not sufficient in the individual cohorts.

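### Response is tested against PD-L1 and CD8 on an undefined positive/negative split although continuous scores are recorded, and CD3 has no response test; a rank-sum test on the score would have more power

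*Combined protocol and SAP*

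**What the plan says.** Section 1.2 sets, in both cohorts, a secondary objective of associating response with PD-L1 expression and with "levels of infiltrating CD3+, CD8+ T-cells and overall response".

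Section 13.8.5 turns this into a two-by-two table in each treatment arm: "Each patient will be retrospectively classified according to pre-treatment PD-L1 expression (positive or negative"), followed by "Clinical response (CR or PR vs. SD/PD/Unevaluable) will be compared according to PD-L1 expression using Fisher's exact tests". Section 13.8.6 does the same for CD8+ cells: "Each patient will be retrospectively classified according to pre-treatment infiltration (positive or negative"). Neither section gives a threshold or, for PD-L1, says whether tumor or stromal cells count. Neither states an alpha level, power or multiplicity rule for these tests. CD3 does not appear in 13.8.6.

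The PD-L1 methods in Section 9 provide staining of tumor and stromal cells, a percentage of positive cells and a modified H-score from 0 to 300. They list published cut-points of 1%, 5% and 50% and continue: "We examine these cut-points in an initial examination of our data". The continuous scores have a limited role: "The percentage of positive staining cells and the modified H-score will also be analyzed as continuous variables for optimized thresholds as exploratory endpoints".

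Elsewhere Section 9 mentions detectable PD-L1 as a hypothesis, and low (0-2) against high (3) lymphocyte groupings used in other studies. Neither is adopted as the rule for the test. For the paired biopsies, 13.8.6 takes a different approach to the same markers, hypothesizing that "PD-L1 expression and T-cell infiltration will increase (measured as a continuous quantitative variable) post therapy", and allows non-parametric tests.

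**The concern.** The objective asks about expression and levels, but the planned test asks about a category that nobody has defined. Two analysts working from 13.8.5 could build different tables from the same slides.

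Responders will be few. At the design rates an arm would have about 9 of 40 (22%), 6 of 30 (20%) or 2 of 40 (5%). With so few, reducing a score to two groups costs power, and that cost is avoidable because the score already exists. Section 9.1.1.1 calls these integrated markers that future trials could use for stratification, so a missed association or an unclear positivity rule would carry forward.

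**Working it through.** **The plan's own figure.** The only power statement for the markers is the paired t-test in 13.8.6: n = 25, a change of 0.59 SD, two-sided 0.05. The noncentrality is 0.59 × √25 = 2.95 on 24 df, which gives power 80.8%. The stated 80% or more reproduces. The association tests have no power figure.

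**Inputs from the documents.** Arms of 40 (NSCLC) and 30 (colorectal). Responders: 0.22 × 40 = 8.8, taken as 9; 0.20 × 30 = 6; 0.05 × 40 = 2.

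**Assumptions.** The marker is normal with SD 1 and is 1 SD higher in responders. The level is two-sided 5%, borrowed from the paired-test statement. All patients have marker data. The documents give no score distribution, so the 1%, 5% and 50% staining cuts are represented by cuts that leave a share q of non-responders positive, with q = 50%, 30% or 15%.

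**Fisher power at one fixed cut.** With r responders and m non-responders, the share positive is q in non-responders and p1 = 1 − Φ(z(1−q) − 1) in responders, that is 0.841, 0.683 and 0.485. Power is the sum over a and b of Bin(a; r, p1) × Bin(b; m, q), taken over tables with Fisher p ≤ 0.05. This is exact.

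**Rank-sum power.** Exact two-sided Wilcoxon test, 10,000 simulated data sets per setting.

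| Patients / responders | Fisher, q = 50% | q = 30% | q = 15% | Rank-sum |
|---|---|---|---|---|
| 40 / 9 | 0.34 | 0.45 | 0.47 | 0.69 |
| 40 / 6 | 0.21 | 0.35 | 0.36 | 0.56 |
| 30 / 6 | 0.16 | 0.34 | 0.38 | 0.50 |
| 40 / 2 | 0.00 | 0.04 | 0.19 | 0.22 |

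Ratios at 40 / 9: 0.69/0.34 = 2.0, 0.69/0.45 = 1.5 and 0.69/0.47 = 1.5. At 30 / 6: 0.50/0.16 = 3.1, 0.50/0.34 = 1.5 and 0.50/0.38 = 1.3.

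**Level.** With no association and 6 or 9 responders, Fisher at one cut rejects in 2% to 3% of data sets and the rank-sum test in 4% to 6%. Against an uncorrected chi-squared test, which runs near 5%, the rank-sum advantage at 40 / 9 falls to about 1.2 to 1.4 times.

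**Scores at the floor.** Section 9 says about 15% of colorectal cancers express PD-L1 in tumor cells. With 85% of scores tied at the floor and the cut at detectable, power at 30 / 6 is 0.33 for Fisher and 0.43 for a tie-corrected rank-sum test, a ratio of 1.3. With half the scores at the floor and 40 / 9 it is 0.39 against 0.67, a ratio of 1.7.

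**Three cuts examined, smallest p taken.** The false-positive rate per arm is 6.1% (40 / 9), 4.8% (40 / 6), 5.4% (30 / 6) and 2.4% (40 / 2). Power is then 0.65, 0.53, 0.52 and 0.21, close to the rank-sum test.

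**The case against.** The strongest reply is that low power and inflated error cannot both apply in full. If one cut is used, Fisher's test is conservative and nothing is inflated. If the best of three is taken, most of the lost power returns and the per-arm error stays near 5%. That stands, and it removes error inflation as a ground for the change.

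A reader might infer from Section 9 that the PD-L1 cut will be the one that looks best in the trial's data. The text does not say so. It names three published cuts in advance, says they will be examined, and labels the optimized thresholds exploratory. A reader might also combine the 120 NSCLC patients, where taking the best of three cuts would give about 9% false positives. Section 13.8.5 plans the test for each treatment arm and contains no pooled test, so that figure does not apply. The three cuts concern PD-L1 only; no CD8 cut is proposed at all.

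It is also fair that a future stratification factor needs categories, and that CD3 and CD8 by multiplex immunofluorescence are listed as optional, so 40 patients with data per arm is optimistic. The first point supports keeping a table and does not defend leaving its rule open. The second lowers power for both tests.

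**Conclusion.** The point holds as a minor improvement to a secondary analysis. The positivity rule is missing for PD-L1 and CD8, the CD3 part of the objective has no response test, and the planned test is less powerful than one available on scores already produced.

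At a 1 SD shift and two-sided 5%, the rank-sum test has about 2 times Fisher's power at a median split and about 1.5 times at the other two cuts (40 patients, 9 responders). It would be too strong to say that a rank test doubles power in general, or that the split discards most of the information. Part of the gain is Fisher's conservatism, the gain shrinks when most scores sit at the floor, and in an arm with about 2 responders neither test can inform. The effect size, the level and the score distribution are assumptions. The primary response comparison and the trial's main conclusion are unaffected.

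**What to change.** In 13.8.5 and 13.8.6, make the planned test an exact, tie-corrected Wilcoxon rank-sum comparison of responders with non-responders, keeping unevaluable patients as non-responders. Apply it to PD-L1 percent positive in one named cell compartment, to CD8 density and to CD3 density, in patients with the assay available, and report how many those are in each arm. State the level and sidedness.

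Keep the Fisher tables as description. Fix one PD-L1 cut and one CD8 cut before marker data are merged with response, and label all other cuts exploratory.

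The cost is a short wording change, with no new samples, assays or visits. The drawback is that a rank test does not itself yield a category for future stratification; the retained table supplies it.
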